11.3	GLOBAL AMENDMENT 3	94
11.4	GLOBAL AMENDMENT 4	96

CTP	Clinical Trial Protocol
CTR	Clinical Trial Report
DILI	Drug Induced Liver Injury
DLE	Dose limiting event
DME	Diabetic macular edema
DMI	Diabetic macular ischemia
DMC	Data Monitoring Committee
DR	Diabetic Retinopathy
DRIL	Disorganisation of retinal inner layer
EC	Ethics Committee
ECG	Electrocardiogram
eCRF	Electronic Case Report Form
eDC	Electronic Data Capture
EMA	European Medicines Agency
EOS	End of study
EoT	End of Treatment
EoTrial	End of Trial
EWOC	Escalation with overdose control
ETDRS	Early treatment diabetic retinopathy study
EudraCT	European Clinical Trials Database
FA	Fluorescein angiography
FAZ	Foveal avascular zone
FSH	Follicle stimulating hormone
FC	Flow Chart
GCP	Good Clinical Practice
GMP	Good Manufacturing Practice
GRT	Global Randomization Team
HCG	Human chorionic gonadotropin
HR	Heart rate
IB	Investigator's Brochure
ICF	Informed Consent Form
ICH	International Council on Harmonisation
IEC	Independent Ethics Committee

IMP	Investigational Medicinal Product
IOP	Intra-ocular pressure
IPD	Important protocol deviation
IRB	Institutional Review Board
IRT	Interactive Response Technology
ISF	Investigator Site File
IUD	Intrauterine Device
IUS	Intrauterine Hormone-Releasing System
IVT	Intravitreal
λ_z	Terminal rate constant of the analyte in plasma
	
LPLT	Last Patient Last Treatment
LOCF	Last observation carried forward
MCH	Mean corpuscular hemoglobin
MCHC	Mean corpuscular hemoglobin concentration
MCV	Mean corpuscular volume
MFD	Maximum feasible dose
MedDRA	Medical Dictionary for Drug Regulatory Activities
MoA	Mode of Action
MD	Multiple dosing
MRT	Mean residence time of the analyte in the body
	
NPDR	Non-proliferative diabetic retinopathy
NOAEL	No observed adverse effect level
Nrp1	Neuropilin 1
OCT	Optical coherent tomography
OCTA	Optical coherent tomography angiography
OPU	Operative Unit
PD	Pharmacodynamic(s)
PDR	Proliferative diabetic retinopathy
	
	
PR	Pulse rate

PRP	Panretinal photocoagulation
PV	Pharmacovigilance
QT	Time between start of the Q-wave and the end of the T-wave in an electrocardiogram
QTc	QT interval corrected for heart rate using the method of Fridericia (QTcF) or Bazett (QTcB)
RA	Regulatory Authority
RDW	Red cell distribution width
REP	Residual Effect Period
RR	Respiratory rate
SAE	Serious Adverse Event
SD-OCT	Spectral domain optical coherence tomography
SMC	Safety Monitoring Committee
SOP	Standard Operating Procedure
SRD	Single-rising dose
SUN	Standardization of Uveitis Nomenclature
SUSAR	Suspected Unexpected Serious Adverse Reactions
█	█
█	█
TS	Treated set
TSAP	Trial statistical analysis plan
█	█
ULN	Upper Level of Normal
█	█
█	█
VA	Visual Acuity
VEGF	Vascular endothelial growth factor
WG	Working group
WHO	World Health Organisation
WOCBP	Woman of childbearing potential
YAG	Yttrium aluminum garnet

1. INTRODUCTION

1.1 MEDICAL BACKGROUND

Diabetic retinopathy (DR) can cause visual loss in a number of ways. Microvascular changes due to hyperglycemia lead to increases in permeability, and thus extravascular exudation and fluid accumulation in the macula (diabetic macular edema, DME). Similarly, alterations of micro-vessels can lead to retinal non-perfusion and ischemia. Consequently, a dramatic increase of vascular endothelial growth factor (VEGF) drives the formation of retinal new vessels (proliferative diabetic retinopathy, PDR), which eventually bleed, and cause a sudden decrease in vision (vitreous hemorrhage). In both conditions, VEGF plays a fundamental role, and anti-VEGF agents are effective in improving both DME and DR. For patients with PDR, panretinal photocoagulation (PRP) is the current standard of care. Patients with severe non-proliferative diabetic retinopathy (NPDR) and a high risk of developing PDR can also benefit from PRP to prevent progression of retinopathy. PRP destroys the ischemic retina, (the major source of VEGF), and thus prevents the formation of new vessels, or promotes their regression.

In some patients, however, in the absence of DME, after successful treatment with PRP, with no evidence of active new vessels, the visual acuity continues to decrease.

[figure not shown]
Some reports have suggested increasing ischemia in the central part of the retina, the macula, as a possible explanation. In this condition, called diabetic macular ischemia (DMI), the retinal tissue may not receive enough nutrients leading to retinal tissue loss and permanent and irreversible vision loss. In DMI, anti-VEGF therapy is not effective, and destructive laser photocoagulation cannot be applied.

Previously, DMI was observed and diagnosed by means of fluorescein angiography (FA) using an intravenous dye. It was defined as an abnormal enlargement of the foveal avascular zone (FAZ). In patients with diabetic retinopathy, FA may show an abnormal enlargement of the FAZ, which is the most common definition of DMI. Recently, optical coherence tomography angiography (OCTA) has emerged which can visualize the retinal blood vessels and hence ischemia in greater detail. OCTA is non-invasive and multiple levels of the capillary plexus can be visualised. OCTA can measure the area of the FAZ. Moreover, the FAZ measured by FA corresponds well with the FAZ measured by OCTA ([R17-3317](#)). For these reasons OCTA is likely to become the gold standard in the diagnosis and monitoring of DMI.

There are many unknowns related to DMI. Since this condition is associated with a progressive loss of neural tissue, it can be hypothesized that restoration of the macular vasculature before retinal degeneration occurs could be a key objective for these patients and prevent permanent vision loss. There are currently no treatments available for DMI making it an urgent unmet need.

1.2 DRUG PROFILE

Mode of action

Safety Pharmacology

The core safety pharmacology function (central nervous, cardiovascular, respiratory systems) were evaluated as part of the 4-week GLP repeat toxicity study in rats, the 13-week GLP intravenous and intravitreal repeat toxicity studies in cynomolgus monkeys, in accordance with the ICH S6 guidelines ([R12-0027](#)).

Overall, BI 765128 did not demonstrate any effects on neurological, cardiovascular, and respiratory function, implicating an acceptable safety profile for Phase 1 clinical trials.

Data from clinical studies

Seven subjects have been treated in part A intravitreally with BI 765128 at the time of finalization of CTP version 4.0. No DLEs, drug-related SAEs or Drug-related AEs were reported.

For a more detailed description of the BI 765128, please refer to the current Investigator's Brochure ([c31489419-01](#)).

1.3 RATIONALE FOR PERFORMING THE TRIAL

Diabetic Macular Ischemia (DMI) is a complication of diabetic retinopathy (DR) and can lead to vision loss. Currently, there are no approved or effective treatments to prevent either onset or progression of DMI in DR patients.

As a transition from preclinical investigations to clinical development in this first-in human trial, the safety, tolerability, pharmacokinetics and early biological response of BI 765128 will be investigated in volunteer subjects with DMI.

This trial will include subjects affected by DMI with significant visual loss since intravitreal injections in subjects without the condition would not be considered ethically justifiable.

This trial will consist of two parts, Part A and Part B.

In Part A of the trial, 3 rising doses (at least 3 evaluable subjects per dose cohort) are planned to be administered intravitreally. Within each dose cohort, all subjects will receive a single dose of BI 765128. The next higher dose will only be administered if the treatment in the preceding dose cohort was safe and showed acceptable tolerability (see section [3.1](#)).

In Part B, subjects will be randomized into a single dose cohort to receive either active IVT injection (n=20) or sham injection (n=10) and assessed over a 20-week period. After an initial active treatment period of 8 weeks [REDACTED] subjects will be followed up for an additional 12 weeks without further injections to study the treatment effect. This may help guide injection frequency intervals in later studies.

Part B will provide information about the early biological response of BI 765128 by comparing the treated group to the sham group.

1.4 BENEFIT - RISK ASSESSMENT

1.4.1 Benefits

DMI is a progressive disease. Patients with DMI may have irreversible retinal damage if DMI is present for a long time. Degeneration of retinal tissue in the macula leads to permanent visual impairment. There is no approved treatment for this disease.

Even though pre-clinical data shows that BI 765128 can improve vascularisation of ischemic areas of the retina, because of the long duration of the pathology of DMI, long-term benefits for subjects entering this trial are unlikely. Their participation in this trial, however, is of major importance to the development of BI 765128, to determine a safe dose selection for further clinical trials in this pre-selected patient population.

1.4.2 Risks

Subjects in this trial are exposed to risks of trial procedures and risks related to ophthalmic and systemic exposure to the trial medication.

1.4.2.1 Risks related to the Mode of Action (MoA)

Because this is the First-in-human trial with BI 765128, special attention will be paid to ensure the highest level of safety for subjects when selecting the starting dose, the dose escalation steps and the highest dose applied. Based on pre-clinical toxicology studies, no specific adverse events are expected. One eye will be selected, according to inclusion /exclusion criteria, as the study eye to be treated.

Similar to other intravitreal biologic therapies, there is a risk of ocular inflammation, however, this is usually mild and reversible. Subjects will be monitored for ocular inflammation and treated if deemed appropriate by the investigator. Because of the low dosage used in intravitreal BI 765128, the systemic exposure is expected to be very low and hence unlikely to have significant effect.

1.4.2.2 Available data from pre-clinical toxicity studies

Toxicology

1.4.2.3 Risks related to intravitreal injection

Intravitreal injections have potentially serious adverse events, but these are considered rare: clinical trials assessing efficacy and safety of EYLEA® intravitreal injections showed serious adverse events related to the injection procedure, including endophthalmitis (in between 0.01 and less than 0.1% of cases) and ocular inflammation (in between 0.1 and less than 1% of cases) ([R20-0435](#)). Because the procedure of intravitreal injection of BI 765128 is the same (use of a filter needle to extract product from the vial and same needle size for injection, 30 gauge), the expected adverse events related to the procedure are considered equal to those observed with marketed drugs (e.g. EYLEA®).

BI recommends the use of material for intraocular drug delivery, which is according to standard medical practice. This material is not officially approved for intraocular drug delivery, with associated potential risks. Long-term experience as standard of medical care suggests a favourable risk-benefit profile. To the best of the sponsor's knowledge there is currently no product on the market, which is officially approved for intravitreal drug delivery.

The needles for preparation of the drug and intravitreal injection are usually silicone oil coated to ease the injection of the needle through the tissue. This carries the potential risk for a silicone oil transfer into the vitreous with the potential risks for occurrence of side effects like vitreous floaters or intraocular inflammation. The overall risk for such events is based on long-term experience with comparable material and is considered low. However, patients should be made aware of this risk, as reflected in the Informed Consent Form (ICF). To the best of the sponsor's knowledge there is currently no product on the market, which is silicone-free. The recommended syringes are silicone oil free and not considered to carry this risk.

The IMP handling instructions do not mandate the use of materials from certain manufacturers and leaves the decision to the treating investigators/sites on which materials to use if it meets the specifications as described in the IMP handling instructions for BI 765128.

1.4.2.4 Risks related to blood sampling

Blood sampling may be accompanied by mild bruising and in rare cases, by transient inflammation of the wall of the vein. In addition, in rare cases a nerve might be injured while inserting the venous catheter, potentially resulting in paraesthesia, reduced sensibility, and/or pain for an indefinite period.

The total volume of blood withdrawn during the entire study per subject will not exceed approx. 500 mL. No health-related risk is expected from this blood withdrawal.

1.4.2.5 Planned measures for monitoring the risks

Subjects will be evaluated with functional, imaging and systemic tests to identify any possible adverse event. Specifically, signs of intraocular inflammation will be assessed by slitlamp examination of the anterior chamber, vitreous and posterior segment of the eye. This will identify flare or cells in the anterior chamber, deposits of material in the corneal endothelium, deposits on the anterior capsule of the crystalline lens, signs of vitreous haze,

vitreous cells, vitreous snowbanks/snowballs, signs of intraretinal edema or retinal thickening and signs of perivascular inflammation e.g. vessel walls sheathing, signs of incipient retinitis or intraretinal haemorrhages.

Spectral domain optical coherence tomography (SD-OCT) will identify possible intraretinal cystic edema and will be used to detect early signs of cell toxicity (e.g. increased ellipsoid zone disruption, granular appearance of outer retinal layers, increase in intraretinal foci predominantly located in the outer nuclear layers). Clinical examination or Color Fundus Photography will be used to identify possible perivascular reactions.

Additionally, a systemic evaluation will be performed at the timepoints specified in the flow charts, to assess possible systemic reactions. This will include body weight, blood pressure, heart rate with ECG, full safety lab. The results of these examinations will be reported immediately to detect possible safety issues related to the drug or to an inflammatory response.

In the first dose cohort (■ mg) the first subject will be dosed and observed until Visit 6 (day 29) to evaluate acute AEs, before dosing the second subject of the same cohort. The second subject will be observed until Visit 6 (day 29) before dosing the third subject of the same cohort. The third subject will be observed until Visit 5 (day 15) before the second dose cohort starts. Details of cohort 2 and cohort 3, see Section 3.1. Moreover, the duration of the observation will reflect the expected human pharmacokinetics (PK) of BI 765128, with a followup for all subjects of up to 98 days, with appropriate ophthalmologic and systemic evaluations (see Section 3.1).

In addition, a Safety Monitoring Committee (SMC) will be established to review individual and aggregated safety data at regular intervals to determine the safety profile and risk/benefit ratio (further details in the SMC charter).

1.4.2.6 Drug induced liver injury

Although rare, the potential for drug-induced liver injury (DILI) is under constant surveillance by sponsors and regulators. Therefore, this trial requires timely detection, evaluation, and follow-up of laboratory investigations of selected liver laboratory parameters to ensure subjects' safety.

Table 1.4.2.6: 1 Overview over trial related risks

Possible or known risks of clinical relevance for this trial	Summary of data, rationale for the risk	Mitigation strategy
Investigational Medicinal Product BI 765128		
Intraocular inflammation	IVT administration of BI 765128 in cynomolgus monkeys showed signs of intraocular inflammation (See IB chapter 5.3) in some animals. These findings in general had no impact on ophthalmic function (i.e. ERG). These are considered ADA responses due to the administration of humanized protein in monkeys and do not predict such reactions in humans.	At each visit a complete ophthalmic examination will be performed to detect early signs of intraocular inflammation (see chapter 1.4.1.4)
Immunogenic response	18 of 22 cyno monkeys showed ADA responses in the 13-week IVT toxicology study of BI765128. The immunogenicity of biotherapeutic products doesn't predict the immunogenicity in human. Therefore, potential immunogenic response may or may not occur in human	██████████ in plasma will be evaluated at day 1,15,29, 57 and 99 in Part A, and at day 1, 29, 57, 85 and 141 in Part B
Drug-induced liver injury (DILI)	This trial is FIH application of BI 765128, and even if the expected systemic exposure is anticipated to be low, any possible effect on liver function needs to be addressed	Lab tests will be performed at each visit (except day 4 in Part A)

Possible or known risks of clinical relevance for this trial	Summary of data, rationale for the risk	Mitigation strategy
Investigational Medicinal Product BI 765128		
Trial procedures		
Risks related to IVT injection	Clinical trials assessing efficacy and safety in marketed drugs administered via IVT injection showed a low rate of complications associated with IVT injection procedure. Because the procedure of intravitreal injection of BI 765128 is the same (use of a filter needle to extract product from the vial and same needle size for injection, 30 gauge), the expected adverse events related to the procedure are considered equal to what was observed with marketed drugs.	At each visit a complete ophthalmic examination will be performed to detect early signs of complications. Intra-ocular pressure (IOP) will be measured at each visit.
Risks related to blood sampling	Blood sampling may be accompanied by mild bruising and also in rare cases, by transient inflammation of the wall of the vein. In addition, in rare cases a nerve might be injured while inserting the venous catheter, potentially resulting in paraesthesia, reduced sensibility, and/or pain for an indefinite period.	The total volume of blood withdrawn during the entire study per subject will not exceed the volume of appr. 500 mL.
Risks related to Anterior Chamber tap	Corneal abrasion, cataract formation, infection, iris and lens trauma	Only experienced physicians will undertake the procedure

1.4.3 Discussion

As this is a first in human trial, ophthalmic and systemic examinations are planned at all visits of the trial, despite no safety concerns being identified from pre-clinical studies.

Blood tests and physical examinations will evaluate potential changes in blood cell count and in any safety lab parameters, as well as in body weight and blood pressure. Ophthalmic physical examinations will focus on the risks related to the procedure (e.g. endophthalmitis) and the risks related to a potential immunologic response. Imaging and functional tests will further assess any possible signs of neurotoxicity after the administration of the drug.

DMI is a potentially blinding disease, with no treatment available. Given the urgent need to address this unmet medical need and considering the expected safety profile of BI 765128 based on pre-clinical evaluations, it is considered acceptable to expose the subjects to the trial risks.

2. TRIAL OBJECTIVES AND ENDPOINTS

2.1 MAIN OBJECTIVES, PRIMARY AND SECONDARY ENDPOINTS

2.1.1 Main objectives

The objective of this trial is to determine the safety and tolerability of BI 765128 in panretinal photocoagulation (PRP) treated diabetic retinopathy (DR) patients with diabetic macular ischemia (DMI), based on the primary endpoint, the occurrence of dose limiting events (DLE) (see Section [5.2.1](#)) in the 7 days post administration (Part A) or the occurrence of drug-related AEs until EOS (Part B) and to investigate the safety, tolerability and early biological response after multiple IVT injections of BI 765128.

2.1.2 Primary endpoint(s)

Part A:

- Number of subjects with ocular dose limiting events (DLEs) from drug administration until day 8 (7 days after treatment)

Part B:

- Number of subjects with drug related AEs from drug administration until EOS

2.1.3 Secondary endpoint(s)

Part A:

- Number of subjects with drug related AEs at EOS
- Number of subjects with any ocular AEs (eye disorders) at EOS

Part B:

- Change from baseline of the size of the FAZ in optical coherence tomography angiography (OCTA) at visit 5
- Change from baseline of the size of the FAZ in optical coherence tomography angiography (OCTA) at visit 6
- Change from baseline of the size of the FAZ in optical coherence tomography angiography (OCTA) at visit 7
- Change from baseline of BCVA at Visit 7
- Number of subjects with any ocular AEs (eye disorders) from drug administration until EOS

3. DESCRIPTION OF DESIGN AND TRIAL POPULATION

3.1 OVERALL TRIAL DESIGN

This trial will consist of two parts, A and B. Part A will be non-randomized, open-label and uncontrolled. Part B will be double-masked, randomized and sham-controlled. One eye will be selected, according to inclusion /exclusion criteria, as the study eye to be treated.

Part A:

Cohorts of subjects will receive escalating doses of BI 765128, [REDACTED]

For any dose-escalation cohort, at least 3 evaluable subjects will be required. Each cohort will consist of newly enrolled subjects.

Dosing of subjects will be done in the following order:

Cohort 1, [REDACTED] (number=3):

- 28 days after subject 1 of the first dose group is dosed, subject 2 of the first dose group can be dosed, if there is no ocular inflammation in the study eye requiring treatment
- 28 days after subject 2 of the first dose group is dosed, subject 3 of the first dose group can be dosed if there is no ocular inflammation in the study eye requiring treatment
- 14 days after subject 3 of the first dose group is dosed, the first subject of the next dose group can be dosed (If no there is no ocular inflammation in the study eye requiring treatment, and if the SMC decides it is safe to go to the next dose group)

Cohort 2, [REDACTED] (number=3):

- 14 days after subject 1 of the second dose group is dosed, subjects 2 and 3 of the second dose group can be dosed (if there is no ocular inflammation in the study eye requiring treatment)
- 14 days after the third subject is dosed, the first subject of the next dose group can be dosed, if there is no ocular inflammation in a study eye requiring treatment, and if the SMC decides it is safe to go to the next dose cohort

Cohort 3, [REDACTED] (number=6):

- 14 days after subject 1 of the third dose group is dosed, subjects 2,3,4,5 and 6 of the third dose group can be dosed, if there is no ocular inflammation in a study eye requiring treatment
- 14 days after the final subject has been dosed, Part B of the trial can start, if there is no inflammation in a study eye requiring treatment, and if the SMC decides it is safe to do so.

A Safety Monitoring Committee (SMC) will be established to regularly review the data and to provide recommendation for the further conduct of the trial.

After each subject has completed visit 4 follow-up assessments (7 days after drug administration), the dosing investigator will complete the 'DLE Safety Review Form' to summarise the key safety findings for the subject. Once completed, the site will send the form to the CTM and CTL.

First 2 subjects in cohort 1 ([REDACTED])

Once the first two subjects have attended visit 6 (day 29), each dosing investigator will complete the 'Ocular Inflammation Review forms'.

Subsequent subjects in part A

Once the following subjects have attended visit 5 (day 15), each dosing investigator will complete an 'Ocular Inflammation Review form' to identify any ocular inflammation. Once completed, the site will send the form to the CTM and CTL. Once the last subject in each cohort has attended visit 5 (day 15), the CTL will forward the 'DLE Safety Review Forms' and the 'Ocular Inflammation Review Forms' for that cohort to other members of the SMC to carefully evaluate all available systemic (i.e. physical examinations, safety lab parameters, ECG and AEs) and ophthalmological (i.e. as defined in section 5.2.1 of the CTP (DLEs)) safety data. The SMC will meet after the last subject of each dose cohort has attended visit 5.

A Bayesian logistic regression model (BLRM), based on a weakly informative prior distribution, and employing the escalation with overdose control (EWOC) principle (see Section 7) will be used for guiding the dose escalation [R13-4803]. After all subjects in a cohort have either experienced a DLE or have been observed for at least the 7 days evaluation period without experiencing a DLE (i.e. 7 days after drug administration, until visit 4, will be evaluated per subject), the BLRM will be updated with the newly accumulated data. The overdose risk will then be calculated for each dose, and escalation will be permitted to all planned doses which fulfil the EWOC criterion and the respective escalation rule.

The BLRM provides estimates for the probability of observing a DLE for each planned dose. Dose escalation will be permitted to the next planned dose which fulfils the EWOC criterion. Note that this may also result in repeating the current dose level, or in going down to a lower dose level again.

If DLEs are observed in the first two consecutive subjects of a previously untested dose level, subsequent enrolment to that cohort will be stopped.

The MFD may be considered reached if all of the following criteria are fulfilled:

- Next recommended dose by the BLRM = current dose
- At least 12 subjects have been treated in the trial
- At least 6 subjects have been treated at the MFD

Part B of the study will only start if the highest dose is tolerated. Once the last subject in the highest dose cohort of Part A has attended visit 5 (day15) the SMC will meet and evaluate all

DLE data as well as available systemic and ophthalmological safety data. The decision on whether to proceed to Part B will be taken based on the occurrence of DLEs.

Part B:

In Part B, the highest dose will be used (██████). Thirty subjects will be recruited, 2:1 ratio of active treatment versus sham. Subjects dosed in Part A of the trial will not be included.

Subjects will be randomized to receive either active treatment or sham injection.

In Part B, subjects will receive three consecutive doses/sham injections over a 3-month period (██████████). All subjects included in the part B of the trial, will be observed for safety and efficacy for 12 weeks after the last injection.

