5.2 ASSESSMENT OF SAFETY

5.2.1 Dose limiting event

A DLE is defined as the occurrence of any of the following events in the study eye within the evaluation period (7 days after drug administration):

- Development of sterile endophthalmitis and/or sterile inflammation of the vitreous of grade 3+ according to the NEI Grading of vitreous haze, and anterior chamber cells of 3+ according to the Standardization of Uveitis Nomenclature (SUN) working group (WG) grading scheme (see Table 5.2.1: 1 below) and a duration of 5 or more days between day 1 and day 8
- Visual loss of more than 15 letters at any given time-point
- Persistent IOP over 30 mmHg for 3 days
- Signs of vascular occlusion in a 1st (the main branch) or 2nd degree (the vessel after the first bifurcation of the main branch) retinal vessel, including peripheral retinal hemorrhages in the area supplied by the occluded vessel (hemorrhage of the macula would not be included as this is a symptom of the disease)

Table 5.2.1: 1 The SUN Working Group Grading Scheme ([R18-1136](#))

Grade	Cells in Field ¹
0	0
0.5+	1-5
1+	6-15
2+	16-25
3+	26-50
4+	>50

¹ Field size is a 1 mm by 1 mm slit beam.

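### In Part A cohorts 2 and 3 the two-consecutive-DLE stop is not guaranteed to spare any planned subject, and the gate after the sentinel does not name DLEs

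*Protocol*

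**What the plan says.** Protocol 3.1 contains a mandatory within-cohort stop: "If DLEs are observed in the first two consecutive subjects of a previously untested dose level, subsequent enrolment to that cohort will be stopped".

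The same section sets the dosing order:

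- **Cohort 1 (3 subjects)** is dosed one at a time: "28 days after subject 2 of the first dose group is dosed, subject 3 of the first dose group can be dosed", subject to there being no ocular inflammation requiring treatment.
- **Cohort 2 (3 subjects)**: 14 days after subject 1, "subjects 2 and 3 of the second dose group can be dosed (if there is no ocular inflammation in the study eye requiring treatment").
- **Cohort 3 (6 subjects)**: 14 days after subject 1, "subjects 2,3,4,5 and 6 of the third dose group can be dosed, if there is no ocular inflammation in a study eye" requiring treatment.

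A DLE (Protocol 5.2.1) is judged over 7 days. Besides severe sterile inflammation it includes "Visual loss of more than 15 letters at any given time-point", intraocular pressure above 30 mmHg persisting for 3 days, and occlusion of a first- or second-degree retinal vessel.

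The DLE Safety Review Form is completed after Visit 4 and sent to the trial manager and trial leader. The forms are passed on only once the last subject of the cohort has reached Visit 5, when the trial leader forwards those "for that cohort to other members of the SMC to carefully evaluate" the safety data. The scheduled SMC meeting follows that visit as well.

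**The concern.** A rule that reacts to the first two subjects can protect the rest only if subject 2's result is known before subject 3 is dosed. Cohort 1 is built that way. Cohorts 2 and 3, at the higher doses of a first-in-human trial, are not: the text sets no interval after subject 2.

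The gate after subject 1 does not close the gap, because it names inflammation requiring treatment and not DLEs. Three of the four DLE criteria are not inflammatory. After a sentinel DLE of one of those three kinds, releasing two more subjects (cohort 2) or five more (cohort 3) could be left to discretion. If all were then dosed together, the two-DLE rule would have no planned subject left to protect.

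**Working it through.** The plan gives no figure for this rule, so there is none to reproduce. The check is a count from the dosing order, a timing comparison, a search for other required holds, and an illustration of size.

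**1. Planned subjects the stop is guaranteed to spare.** Suppose all permitted subjects are dosed on the first permitted day.

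| Cohort | Planned | Can be dosed before subject 2's 7-day result | Remaining after subject 2 | Guaranteed spared |
|---|---|---|---|---|
| 1 | 3 | 2 | 1 | 1 |
| 2 | 3 | 3 | 1 | 0 |
| 3 | 6 | 6 | 4 | 0 |

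**2. Timing of the sentinel's result.** Visit 4 is day 8 ± 2 (Flow Chart I), so it ends by day 8 + 2 = 10. Release is 14 days after day 1, that is day 15. The sentinel's DLE status should therefore be known at least 15 − 10 = 5 days before release. The information exists in time, but no text makes it a condition of release.

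**3. Other provisions that might force a hold after one sentinel DLE.**

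- Protocol 3.3.4.3: halts on one serious, or two severe, adverse reactions, with causality confirmed by both investigator and sponsor. One non-serious DLE, or one not confirmed as related, does not meet it.
- Protocol 5.2.7.1.4 and 5.2.7.2.2: a DLE is an AESI, reported within 24 hours. This is reporting, not a hold.
- Protocol 3.3.4.1 and 7.3.7: the sponsor may pause treatment and monitors safety continuously. The pause is discretionary.
- Protocol 3.1: the BLRM update and scheduled SMC meeting come after the whole cohort has been dosed.
- Protocol 8.7: SMC procedures are in a charter that was not available.

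**4. Illustration of size.** The inputs are the true DLE rates in Table 10.3: 2, taking its second and third columns as doses 2 and 3. The headers are redacted, but the scenario 1 values match the prior means in Table 7.1: 2. With independent subjects, P(first two both have DLEs) = p², conditional on reaching the cohort.

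| Scenario | Cohort 2 | Cohort 3 |
|---|---|---|
| 1 (prior mean) | 0.073² = 0.5% | 0.153² = 2.3% |
| 2 (high) | 0.173² = 3.0% | 0.243² = 5.9% |
| 4 (very high) | 0.353² = 12.5% | 0.564² = 31.8% |

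Given that event in cohort 3, the expected further DLEs among the four unspared subjects are 4p: 4 × 0.153 = 0.61 in scenario 1 and 4 × 0.564 = 2.26 in scenario 4.

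These rates cover every DLE type. The share that is inflammatory, or serious and related, and so already held, is not given. The figures therefore do not measure the unguarded gap.

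**5. The trial's own model after one sentinel DLE.** The BLRM was rebuilt on a grid from the Table 7.1: 1 prior. Doses are redacted. Assumed ratios of 0.2 : 0.4 : 1 give prior means of 0.054, 0.073 and 0.153, as stated, and P(rate ≥ 0.25) of 0.050, 0.072 and 0.190 against the stated 0.050, 0.073 and 0.190. The ranges below vary the middle ratio from 0.3 to 0.5.

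- Top dose after 0/3, 0/3 and 1/1: P(rate ≥ 0.25) = 0.37 (0.35 to 0.38), above the 0.25 EWOC limit.
- Middle dose after 0/3 and 1/1: 0.20 (0.17 to 0.22), below the limit.

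EWOC applies between cohorts, so this is only a yardstick. By it, one sentinel DLE would matter at the top dose but not at the middle dose.

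**The case against.** The strongest reply is that little is left to protect. Protocol 1.2 states "Seven subjects have been treated in part A intravitreally with BI 765128 at the time of finalization of CTP version 4.0" and "No DLEs, drug-related SAEs or Drug-related AEs were reported". SAP 7 describes the BLRM evaluations after each Part A dose group in the past tense. Both points stand and limit the practical effect.

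The dosing intervals in Part A were extended after authority feedback (Protocol 11.1), so the staggering was considered. That is true, but the current text still gives cohorts 2 and 3 no interval after subject 2.

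The gap is also narrow. Serious related reactions halt entry, and DLEs reach the sponsor within 24 hours. At the middle dose the trial's own overdose criterion would still pass after a single sentinel DLE. All of this stands. What remains is a non-inflammatory DLE that is non-serious or not confirmed as related, for which the protocol requires no hold.

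A reader might infer that the stop can never work in cohorts 2 and 3. The documents do not support that. Group dosing is permitted, not required, so slow recruitment could stagger subjects and let the stop act. It can also act on replacement subjects (Protocol 3.3.5) and on subjects the SMC adds (Protocol 7.1). Zero spared is the permitted worst case.

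**Conclusion.** The point holds as a limited weakness in the protocol text. In cohorts 2 and 3 the two-DLE stop is guaranteed to spare 0 of 1 and 0 of 4 remaining planned subjects, and a sentinel DLE that is neither inflammatory nor serious and related triggers no required hold in the protocol. This rests on reading the permission to dose at face value and on the protocol alone, since the SMC charter may add a hold.

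Two stronger inferences should be resisted. The 12.5% and 31.8% are not the probability that subjects go unprotected: they come from the most toxic simulated scenario, are conditional on reaching the cohort, and include DLEs that are already held. Nor do the documents show that the gap ever operated: no DLE had been reported in the first seven subjects, and Part A appears to be finished. The point merits consideration but is of low practical weight.

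**What to change.** In Protocol 3.1, for any cohort or any repeated or intermediate dose level still to be dosed, change the within-cohort gate to require no ocular inflammation needing treatment **and no DLE as defined in 5.2.1**. If the sentinel has a DLE, require SMC review before further dosing. If the SMC allows dosing, dose subject 2 alone until Visit 4, so that the two-DLE stop can act. A triggered stop would then spare 1 of 3 subjects in cohort 2 and 4 of 6 in cohort 3.

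Cost: no waiting time unless a sentinel DLE occurs, because Visit 4 closes by day 10 and release is on day 15. After a sentinel DLE, the cost is an ad hoc SMC review plus about one week (Visit 4 falls 5 to 9 days after dosing). If Part A is still open, a protocol amendment with its approvals is needed. No extra listing of dosing dates is required, since SAP 7.7 already lists the date and time of each administration.
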